4.2 Exclusion Criteria

Subjects meeting any of the following criteria will be excluded from the study:

- 1. Subject has evidence of a serious active infection.
- 2. Systemic or topical retinoids or other topical medications, not including emollients, within the past 30 days Baseline Visit 1.
- 3. Subject has received an investigational systemic or topically administered drug within the past 30 days prior to Baseline Visit 1.
- 4. Subject is currently taking and was unwilling or unable to discontinue any medication excluded in Section 5.7.1.
- 5. Subject is currently receiving immunosuppressive therapy, including intermittent or low-dose systemic corticosteroids.
- 6. Subject has a known allergic reaction to any ingredients of study drug formulation.
- 7. Subject has a history of any malignancy.
- 8. Subject is known to be human immunodeficiency virus positive or had other known immunodeficiency.
- 9. Subject has clinically significant laboratory test abnormalities or a history of any other condition that, in the opinion of the Investigator, could compromise the subject's ability to

comply with the protocol or that could compromise the subject's safety or the interpretation of the study results.

- 10. Subject is currently participating in any other therapeutic clinical study.
- 11. Subject is pregnant or lactating.

4.3 Subject Withdrawal and Replacement

Subjects and caregivers will be informed that they have the right to withdraw the subject from the study at any time for any reason, without prejudice to their medical care. The Investigator also has the right to withdraw subjects from the study for any of the following reasons:

- Progression of disease that, in the opinion of the Investigator, precludes further study drug treatment,
- Development of an unacceptable AE or SAE,
- Subject or Sponsor request,
- Subject non-adherence to study drug dosing or protocol requirements, or
- Pregnancy.

The reason for study withdrawal is to be documented in the subject's source documents and CRF. Withdrawn subjects may be replaced at the discretion of the Sponsor.

Subjects who prematurely discontinue from the study should be seen as soon as possible for Week 24 assessments (Part 1:Table ; Part 2:Table 2).

For subjects who are lost to follow-up (i.e., those subjects whose status is unclear because they fail to appear for study visits without stating an intention to withdraw), the Investigator should show due diligence by documenting in the source documents all steps taken to contact the subject (e.g., dates of telephone calls, registered letters, etc.).

5 STUDY TREATMENT

5.1 Description of Study Treatment

5.2 Packaging and Labeling

Labels will be in the local language and comply with the legal requirements of each country. Clinical supplies are to be dispensed only in accordance with the protocol. Study drug labels will not bear any statement that is false or misleading in any manner or represent that the study drug is safe or effective for the purposes for which it is being investigated.

5.3 Study Drug Storage

Study drugs must be received by a designated person at the study site, handled and stored safely and properly, and kept in a secured location.

5.4 Study Drug Accountability

The Investigator or designee will maintain accurate records of receipt and condition of study drug, including dates of receipt. In addition, accurate records will be kept of the date dispensed, quantity dispensed, and the subject to whom study drug was dispensed. Any reasons for departure from the protocol-specified dispensing regimen must also be recorded.

The Investigator or designee is responsible for monitoring the inventory of study drug and for the accountability of all used and unused study drug. Drug accountability will be verified by the study monitor during site visits and at the completion of the trial.

Refer to the Pharmacy Manual for additional details.

5.5 Study Drug Retention

Study drug must be retained until completion or termination of the study, and written authorization from the Sponsor has been received. All unused and used study drug should be destroyed at the site or returned to the distributor, as specified by Sponsor. It is the Investigator's responsibility to ensure that the Sponsor has provided written authorization prior to return or destruction, and that appropriate records of the disposal are documented and maintained. No used or unused study drug may be disposed until fully accounted for by the study monitor.

5.6 Treatment Administration

The target efficacy and treatment areas will be identified by the Investigator as noted below. The Investigator will apply the initial dose of study drug and at designated timepoints when study drug will be applied to expanded treatment areas. These applications will be observed by the subject and caregiver at the study center. Thereafter, subjects or caregivers will apply subsequent doses throughout the duration of the study.

A standard amount of study drug for the percent BSA under treatment will be measured and applied to the treatment area once daily to achieve a dose of approximately 8 mg/cm², with each application administered approximately 24 hours apart. Study drug should only be administered to the treatment area, as directed by the Investigator, during the study.

Subjects or caregivers are required to wear protective gloves during application and thoroughly wash their hands after application to prevent study drug exposure.

At scheduled study visits at the site, subjects may not bathe or apply study drug or as-needed topical symptom control therapy (emollients) to the treatment area within 12 hours of examination or photographic assessment. Subjects should refrain from applying as-needed topical symptom control therapy and bathing within 4 hours of applying study drug to the treatment area. The treated area should be covered by loose clothing to minimize light exposure.

Target Efficacy Area used for the primary endpoint assessment in Part 1 and Part 2 will be based on one of the body sites as defined in the VIIS tool (upper back, upper arm or lower leg/shin)¹ that has a VIIS scaling severity score of Grade 2 or higher as assessed by the Investigator. The body

¹ Dorsal foot cannot be selected as the target efficacy area.

site with the worse VIIS scaling severity score should be selected, if applicable. The target efficacy area will be used for all efficacy analyses.

Treatment Area will be determined by the Investigator as follows:

In Part 1, the initial treatment area will be defined as approximately 20% BSA with Grade 2 or higher on the VIIS scaling severity score, on one-half of the body, left or right side, and will include the target efficacy area. From Week 1 through Week 12, study drug will be applied in the initial treatment area.

If the Investigator determines that there are no safety or tolerability issues at the end of Week 12, the treatment area will increase to all of the affected areas of ichthyosis on one-half of the body (approximately 40-45% BSA in a typical SLS patient), left or right side. From Week 13 through Week 20, the study drug will be applied to the extended treatment area affected by ichthyosis.

If there are still no safety or tolerability issues at the end of Week 20, the treatment area will further increase to all affected areas of ichthyosis on the entire body (approximately 80-90% BSA in a typical SLS patient). From Week 21 through Week 24, the study drug will be applied to the entire body affected by ichthyosis.

For example, if the left lower leg is determined by the Investigator to be the target efficacy area, then the entire left leg would likely be defined as the initial treatment area. At the end of Week 12, if there are no safety or tolerability issues, the treatment area would extend to the entire left side of the body. At the end of Week 20, if there are no safety or tolerability issues, the treatment area would include the entire body.

In Part 2, the treatment area will be defined as all affected areas of ichthyosis on the body (approximately 80 - 90% of BSA in a typical SLS patient). Subjects will be treated for 24 weeks followed by a safety follow-up visit 4 weeks after the end of dosing.

Refer to the Pharmacy Manual for detailed information regarding treatment administration.

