	Screening ¹	Baseline Visit 1 ¹	Visit 2	Visit 3	Visit 4	Visit 5	Visit 6	Visit 7	ET Visit 8 ²	Safety Follow-up Visit 9
	Day -7 to -1	Week 1 Day 1	Week 1 Day 2	Week 4 ± 3 days	Week 8 ± 5 days	Week 12 ± 3 days	Week 16 ± 5 days	Week 20 ± 3 days	Week 24 ± 5 days	Week 28 ± 5 days
Evaluation	Site Visit	Site Visit	Site Visit	Telephone	Site Visit	Telephone	Site Visit	Telephone	Site Visit	Site Visit
Informed consent / assent	Х									
Eligibility review	Х	Х								
Demographics / medical history	Х									
Concomitant medications	Х	Х	Х	Х	Х	Х	Х	Х	Х	X
Adverse events	Х	Х	Х	Х	х	х	х	х	Х	x
Urinalysis / pregnancy test ³	Х	Х			Х		Х		Х	
12-Lead ECG (see Table 1-1)	Х	Х			Х				Х	
Holter Monitoring		Х			Х				Х	
Vital Signs (see Table 1-1)	х	Х	Х		Х		Х		х	
Physical exam ⁴	Х	Х	Х		Х		х		Х	
Dermatologic exam	х	Х	Х		Х		Х		х	Х
Digital photography⁵		Х			Х		х		Х	Х
VIIS (Investigator-assessed)		X ⁶	Х		х		х		Х	Х
Global impression of severity		Х			Х		х		Х	Х
Patient/Observer-reported scales ⁷		Х			Х		Х		х	х
PD sample collection ⁸		Х	Х		Х		Х		х	
Clinical laboratory testing ⁹	х	Х			Х		Х		х	
PK sample collection ¹⁰ (see Table 1-1)		Х	Х		Х		Х		Х	
Randomization		Х								
Administer study drug ¹¹		Х	Х	Х	Х	Х	Х	Х		
Dispense study drug & diary			Х		Х		Х			
Collect study drug & diary					Х		Х		Х	
Exit interview									X ¹²	

ECG = electrocardiogram; ET = early termination; PD = pharmacodynamic; PK = pharmacokinetic; VIIS = Visual Index for Ichthyosis Severity

1. Samples collected for urinalysis and clinical laboratory tests may be analyzed at a local lab.

- 2. Subjects who terminate early from the study will undergo, if possible, all of the assessments and procedures scheduled for Visit 8 (Week 24).
- 3. Urine pregnancy test for female subjects of child-bearing potential only. Tests can be analyzed at the study site.
- 4. Complete physical exam, including height and weight collection, performed at Screening Visit only; symptom directed physical exams at all other timepoints.
- 5. Subjects should refrain from bathing and applying study drug or as-needed topical symptom control therapy (emollients) to the treatment area within 12 hours of obtaining digital photographs.
- 6. VIIS must be independently assessed by two different Investigators at Baseline Visit 1 only.

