6.12 Dermatologic Exam

A complete dermatological exam will be performed during the designated study visits.

The VIIS scaling severity scale will be utilized to document ichthyosis.

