10.1 Sample Size

Part 1 of the study will assess the effect size on the VIIS scaling severity score with ADX-102 1% topical dermal cream, and will confirm the sample size needed for Part 2. Part 2 is expected to require approximately 30 subjects.

The approximate number of 30 subjects for Part 2 was based on the NS-003 Phase 2 study which used the ISS endpoint. The mean ISS Scaling sub-score change from baseline was -0.7 with a standard deviation of 0.52. Conservatively, the change was set to -0.5 and the standard deviation to 0.6. A sample size of 20 achieves 94% power to detect a difference of 0.5 between the null hypothesis mean of 0.0 and the alternative hypothesis mean of -0.5 with an estimated standard deviation of 0.6 and with a significance level (alpha) of 0.05 using a two-sided one-sample t-test. If the above assumptions remain, except that the standard deviation is increased to 0.7, then a sample size of 20 achieves a power of 85%. The sample size of 30 is therefore based on these estimates requiring 20 subjects to be treated with ADX-102 1%. As subjects will be randomized in a 2:1 ratio, 10 subjects will be treated with vehicle.

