5.7. ADMINISTRATION OF STUDY MEDICATION

A standard amount of study drug for the percent BSA under treatment will be measured and applied to the treatment area once daily to achieve a dose of approximately 8 mg/cm2, with each application administered approximately 24 hours apart. Study drug should only be administered to the treatment area, as directed by the Investigator, during the clinical trial.

The Target Efficacy Area used for the primary endpoint assessment in Part 1 will be based on one of the body sites as defined in the VIIS tool (upper back, upper arm or lower leg/shin) that has a VIIS scaling score of Grade 2 or higher as assessed by the Investigator. The body site with the worst VIIS scaling score should be selected, if applicable. The target efficacy area will be used for all efficacy analyses; for all other treated areas, data will be summarized.

Syneos Health #1009367

The Treatment Area will be determined by the Investigator as follows:

In Part 1, the initial treatment area will be defined as approximately 20% BSA with Grade 2 or higher on the VIIS scaling score, on one-half of the body, left or right side, and will include the target efficacy area. From Week 1 through Week 12, study drug will be applied in the initial treatment area.

If the Investigator determines that there are no safety or tolerability issues at the end of Week 12, the treatment area will increase to all of the affected areas of ichthyosis on one-half of the body (approximately 40-45% BSA in a typical SLS patient), left or right side. From Week 13 through Week 20, the study drug will be applied to the extended treatment area affected by ichthyosis.

If there are still no safety or tolerability issues at the end of Week 20, the treatment area will further increase to all affected areas of ichthyosis on the entire body (approximately 80-90% BSA in a typical SLS patient). From Week 21 through Week 24, the study drug will be applied to the entire body affected by ichthyosis.

For example, if the left lower leg is determined by the Investigator to be the target efficacy area, then the entire left leg would likely be defined as the initial treatment area. At the end of Week 12, if there are no safety or tolerability issues, the treatment area would extend to the entire left side of the body. At the end of Week 20, if there are no safety or tolerability issues, the treatment area would include the entire body.

Syneos Health #1009367

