8.4. KEY DEFINITIONS AND TERMINOLOGY

Reference start date and study day

Study Day will be calculated from the reference start date and will be used to show start/stop day of assessments and events.

Baseline Value

For purposes of analysis, the baseline value is defined as the last non-missing value obtained prior to initiation of study drug.

Change from Baseline.

Change from baseline for a given endpoint is defined as the difference between a post-treatment study day value and the baseline variable value and will be calculated directionally as post-study minus baseline.

Note that for the VIIS, it is planned that a single investigator will complete this instrument prior to randomization on day 1 of Part 1.

Day 1 (Baseline)

Day 1 is the earliest day that the study drug is first initiated.

Age

Syneos Health #1009367

Age is calculated as the number of whole years from a subject's date of birth to the date of informed consent.

Study Visit.

Study visit is the nominal visit as recorded on the eCRF.

Total Days on Study

Total days on study is defined as the number of days from Day 1 to the date of completion or early termination.

Last Dose of study drug

Last dose of study drug is defined as the number of days from day 1 to the date of last dose of study drug.

Duration of SLS.

The duration of SLS is defined as the number of whole years from the date of onset of SLS diagnosis to the date of informed consent.

Adverse Event

An adverse event is any untoward medical occurrence in a patient or clinical investigation patient, temporally associated with the use of a medicinal product, whether or not considered related to the medicinal product.

Treatment Period

The Treatment Period covers the duration that a patient is in the study from Baseline (Day 1) to Week 24.

Safety Follow-up Period

The Safety Follow-up Period continues for 28 days after the last dose of study treatment at Week 24 through Week 28.

Definition of Study Completion

A patient will be defined as "completed" if she or he completes the Week 24 study visit.

End of Study Definition

Syneos Health #1009367

End of study is defined as the date when the patient has completed one of the following: completed the follow-up visit after the Week 24 visit, permanently discontinued from the study, or lost to follow-up.

Day of Study Termination

Day of study termination = Termination Date - Date of Baseline (Day 1) + 1.

Percent Change from Baseline

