These analyses will be carried out in an analogous fashion as for the primary efficacy variable (see above for a description of each analysis applied to the primary efficacy variable).

As with the primary efficacy variable (VIIS scaling), the within-group change from baseline will be the primary focus of interest in the MMRM analysis. Because SLS patient symptoms do not spontaneously improve over time, the within-group comparison provides a clinically meaningful evaluation. The planned analyses for selected secondary efficacy endpoint are outlined in Table 10.2.2.

Table 10.2.2: Analyses of the Secondary Efficacy Variables

	Analyses			
Secondary Efficacy Variable	MMRM	RESPONDER ANALYSIS (Estimating Equation)	AUC (Linear Model)	Survival
VIIS Erythema (Investigator Assessment)	✓		√	✓
VIIS Scaling (Photographic Assessment by Central Reader)	✓	✓	✓	✓
VIIS Erythema (Photographic Assessment by Central Reader)	✓		√	√

¹The 100 mm VAS will be analyzed using MMRM. Categorical outcomes will be displayed in a contingency table (Treatment x Category) containing frequency and percent occurrence of categorical outcomes.

²The total score (i.e., sum of 0 - 3 rating on 10 individual questions) will be analyzed using MMRM for change scores and a linear model for AUC. Responses to individual questions will be provided in a listing.

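### The plan does not separate the VIIS reading that selects the worst-scoring target site from the reading used as baseline, so regression to the mean can pass for improvement in the within-arm test

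*Protocol*

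**What the plan says.** **Site selection.** Under Protocol 5.6 the target efficacy area is the upper back, upper arm or lower leg, at Grade 2 or higher on VIIS scaling, and the body "site with the worse VIIS scaling severity score should be selected, if applicable". SAP 5.7 agrees: "The body site with the worst VIIS scaling score should be selected, if applicable". The collection form in SAP 20.2 scores left and right separately, so there are three candidate sites, or six if sides count.

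**Baseline.** Protocol Tables 1 and 2 first schedule the Investigator VIIS at Baseline Visit 1. SAP 8.4 takes the last value before study drug as baseline and adds for Part 1 that "it is planned that a single investigator will complete this instrument prior to randomization on day 1 of Part 1". For Part 2, footnote 6 to Protocol Table 2 states: "VIIS must be independently assessed by two different Investigators at Baseline Visit 1 only". Protocol 6.9 also asks for two raters. Neither place says what each reading is for.

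**Test.** Protocol 10.1 sizes Part 2 on the drug arm alone, "with a significance level (alpha) of 0.05 using a two-sided one-sample t-test". Protocol 10.4 allows a claim if the 95% CI lies above zero, its midpoint is at least 0.5, and at least half of subjects improve by one grade or more. It does not name the arm. I read it as the drug arm, because of the sizing and because 10.4 does not expect the vehicle contrast to reach significance. SAP 10.1 analyses drug-treated subjects only and succeeds on a significant negative Visit 8 term. Protocol Section 10 makes starting Part 2 depend in part on a mean active change near or above 0.5.

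**Justification.** SAP 10.2: "Because SLS patient symptoms do not spontaneously improve over time, the within-group comparison provides a clinically meaningful evaluation".

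**The concern.** A whole-grade visual score carries rating error. A site picked because its reading was the highest of several carries, on average, error in the upward direction. Rated again, it tends to score lower although the skin is unchanged. If the selecting reading is also the baseline, that drop enters the change score as improvement.

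The SAP's argument that symptoms do not improve by themselves concerns natural history. It does not concern selection on an imperfect measurement. Including baseline as a covariate does not remove the bias from a one-arm mean. Randomisation would be expected to balance it between arms, so that it cancels in the drug-minus-vehicle contrast, but the decision rules do not use that contrast. The Part 1 success rule, the decision to start Part 2 and all three parts of the Part 2 claim rule take zero change as the null state, so the bias pushes each of them towards success.

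**Working it through.** **1. The plan's own figure.** Inputs from Protocol 10.1: n = 20, two-sided alpha 0.05, one-sample t-test. On effect and spread it says: "Conservatively, the change was set to -0.5 and the standard deviation to 0.6"; the alternative SD is 0.7. Power from the noncentral t distribution with 19 df and noncentrality (0.5/SD) × √20 is 94.2% at SD 0.6 and 85.8% at SD 0.7. The stated 94% and 85% reproduce.

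**2. What a given bias does to the same test.** With no drug effect but a mean shift b, the chance that the CI excludes zero in the drug's favour is the upper tail of the noncentral t with noncentrality (b/SD) × √20. Nominal is 2.5%.

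| b | SD 0.6 | SD 0.7 |
|---|---|---|
| 0.1 | 10.5% | 8.8% |
| 0.2 | 29% | 23% |
| 0.3 | 56% | 44% |

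For example, b = 0.3 at SD 0.6 gives noncentrality (0.3/0.6) × 4.472 = 2.24, hence 56%.

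**3. How large b could be.** The documents give no VIIS reliability, so everything here is assumed: true severity mean 2.8, between-subject SD 0.6, between-site SD 0.4, readings rounded to whole grades 0 to 4, independent errors, no drug effect, worst site taken with ties broken at random, Grade 2 floor applied. Error variance is (0.6² + 0.4²) × (1 − ICC)/ICC; at ICC 0.8 that is 0.52 × 0.25 = 0.13. Change is selecting reading minus Week 24 reading, with improvement positive, in simulated groups of 20. The claim rule is read in the improvement direction, since the SAP codes improvement as negative.

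One reading selects and is baseline, three sites:

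| ICC | Spurious improvement | CI excludes zero | Full claim rule met |
|---|---|---|---|
| 0.9 | 0.17 | 33% | 0.4% |
| 0.8 | 0.25 | 42% | 4% |
| 0.7 | 0.33 | 52% | 13% |
| 0.6 | 0.41 | 62% | 27% |

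With six sites, at the same ICCs, spurious improvement is 0.25, 0.36, 0.47 and 0.58. The full rule is met in 2%, 17%, 39% and 61%, and the CI excludes zero in 61% (ICC 0.9) to 92% (ICC 0.6).

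**4. Other uses of the readings.** If the average of two readings both selects and is baseline, the bias is still 0.11 to 0.39 and the CI excludes zero in about 18% to 69% across three and six sites. If one reading selects and an independent reading is baseline, the mean change is 0.00 and the CI excludes zero in about 2.5%. The floor alone, with one site fixed in advance, adds only 0.02 to 0.08. Choosing the worst site is the main source.

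**5. Cross-check on a second set of assumptions** (mean 2.7, between-subject SD 0.5, between-site SD 0.4). Where the error SD (0.35 to 0.5) gives a change SD of 0.58 to 0.73, close to the planned 0.6 to 0.7, the bias is 0.25 to 0.52, the CI excludes zero in 41% to 89% and the full rule is met in 3.5% to 53% (three and six sites together).

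**6. Sensitivity to the error model.** Three sites, full rule at ICC 0.8, 0.7 and 0.6:
- 1%, 5%, 13% if one region is on average 0.7 grade worse than the others;
- 2%, 5%, 12% if half the error variance is shared across sites;
- 0.4%, 1.5%, 4% if half is a stable tendency of the rater at that site, which repeats at Week 24 and so drops out of the change.

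In the last case, over ICC 0.9 to 0.6, the full rule is met in 0% to 4% with three sites and 0.2% to 14% with six.

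**The case against.** A reader might infer that one Day 1 reading selects the site, applies the floor and serves as baseline throughout the trial. The documents do not say so. For Part 1 it is the likeliest reading, not a stated one. For Part 2, the only part that supports a claim, it does not fit: two independent baseline readings are required. Eligibility is also reviewed at Screening, and of the dermatologic exam done there Protocol 6.12 says: "The VIIS scaling severity scale will be utilized to document ichthyosis". The form in SAP 20.2 speaks of a site already selected. All this stands. It shows that a separate selecting reading is possible, but nothing requires one.

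A reader might also take the CI percentages as the false-claim rate. They are not. The midpoint and responder conditions give real protection, and the full rule is barely inflated at high reliability with three sites. The independent-error model is also the unfavourable one. Both points stand.

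The plan has partial safeguards. Central-reader VIIS scaling is a secondary endpoint (SAP 6.2), and nothing gives that reader a part in selection. SAP 10.4 allows combined-region, contralateral and vehicle-inclusive exploratory analyses. Protocol 10.4 reports the vehicle contrast, although 20 against 10 has only about 58% (SD 0.6) or 45% (SD 0.7) power for a difference of 0.5. These could reveal the artefact, but they do not alter the primary test.

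Finally, Part 1 makes no efficacy claim, and SAP 8.2 treats its significance levels as an additional index. That lowers the stakes there, but the Part 1 mean change still informs the decision to start Part 2.

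**Conclusion.** The gap is real: the worst site is chosen, a floor is applied, change is tested against zero within the drug arm, and no rule keeps the selecting reading apart from the baseline. In Part 2 the roles of the two baseline readings are undefined. If one reading or their average does both jobs, the test against zero is biased towards improvement at every reliability examined. The full claim rule is affected much less, from negligible to substantial depending on reliability, number of candidate sites and how much rating error is stable. These are conditional figures, because the documents give neither VIIS reliability nor between-site spread.

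It would go too far to say that the Part 2 claim rule is shown to be invalid, or that the biased procedure is prescribed. The plan permits it and does not exclude it. This should be fixed; the direction of the bias is clear, its size is not.

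**What to change.** **Part 2.** State in Protocol 5.6 that the second Investigator's independent Day 1 VIIS selects the target efficacy area and applies the Grade 2 floor. The first Investigator's Day 1 score at that site is then the baseline, whatever its value, and the first Investigator also rates Week 24 where possible. Both readings are already scheduled. All affected skin is treated in Part 2, so the choice of site does not change treatment. Averaging the two readings for both jobs is not a remedy. Screening grades could select instead only if site-level VIIS grades are actually recorded then: Table 2 schedules no VIIS at Screening, and SAP 11.7 classifies the dermatologic exam as normal or abnormal by broad region.

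**Part 1.** SAP 8.6 describes conduct in the past tense, so the remedy is analytic. Repeat the primary analysis with the Visit 2 VIIS at the target area as reference, and report the Day 1 to Day 2 change by arm.

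**Cost.** A short addition to Protocol 5.6 and one extra analysis with a table. Observed changes will be somewhat smaller, and a few subjects may have a baseline below Grade 2. Same-day ratings do not remove day-to-day fluctuation. Any systematic difference between the two raters stays out of the change score only if one rater supplies both baseline and Week 24. The Visit 2 reference follows one application, and a rater who recalls Day 1 may make the selection effect look smaller than it is.
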